- a. Lengthen the time window of treatment for patients with fCIS from 6 hours to 24 hours. In doing so, we will offer useful treatment to patients who would otherwise be denied treatment under current standards.
- b. Encourage focusing on achieving good revascularization rather than limiting time during IAT for patients with fCIS.
- c. Improve the percentage of good outcomes in the treated population
- d. Save patients with pCIS from complications due to brain edema and intra-cranial hemorrhage that could potentially result from IAT
- e. Save the health care system the costs of futile treatment of patients with pCIS.

III. METHODS

A. Study Design:

Version: 6.0

The current study focuses on patients with acute ischemic stroke due to a blockage of the intracranial internal carotid artery or middle cerebral artery (M1). The study will be performed prospectively in up to 6 stroke centers. Akron General Medical Center is the primary institution for development of the study and data analysis for this multicenter trial. To participate in the study, all centers need to meet certain qualified requirements which include:

- One neurointerventionalist with 6 years' experience in performing IAT with multiple devices.
- Demonstrate coverage of the comprehensive stroke center 24 hours a day. The proposed study will be carried out over a period of 4 years from the initial approval date. Informed consent will be obtained for each patient, as described in section VIII. The study will be carried out in 2 phases (Figure 1).

Phase I will compare outcomes between treated patients with fCIS and pCIS. All eligible patients will be assessed by a full diagnostic cerebral angiogram with dye injection of all potential collaterals. DCA will be used to characterize the CIS. Treatment will be identical for both groups. All patients will be treated with the combination of IAT and the normal standard of care for a patient not receiving IAT (which may include IVT, but not always). The sample size will be set to have 60 patients complete the trial. Distribution of fCIS and pCIS patients will not be forced, but the option to balance groups may be employed if the percentage for one group reaches 70%.

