The population for the study will be patients with anterior circulation acute ischemic stroke due to blockage of the intracranial internal carotid artery or middle cerebral artery (M1) within 8 hours of onset of symptoms. Typically, IAT is only offered to patients up to 6 hours, with no treatment options directly targeting the clot available after that time. Occlusion of one of these vessels will be determined based on CT angiography, magnetic resonance angiography, or DCA. Only patients 18 or over will be considered for the study. Other inclusion criteria include a score of 8 or greater on the National Institute of Health Stroke Scale (NIHSS, see appendix). Exclusion criteria will include contra-indication for IAT found on initial CT, intracranial hemorrhage, stroke mimics (tumor, herpetic encephalitis, etc.), more than 1/3 hypodensity on non-enhanced head CT prior to intervention, ASPECT Score < 6, and pre-existing disability defined as mRS ≥ 2. Pregnant women will also be excluded.

[figure not shown]

Figure 1: Study design for Phase I

Version: 6.0 5

[figure not shown]

Figure 2: Study design for Phase II

C. Assessment of Resources

The multicenter study will be carried out at up to 6 stroke centers. Each center is expected to have approximately 1 patient per month eligible for the study. Enrollment of patients will be performed at the end of imaging at each institution. At Akron General Medical Center, consent will be obtained within the DCA imaging suite. Consent will be obtained by a person qualified by the local IRB other than the treating physician. At Akron General, consent will be acquired by one of two neurointerventional lab nurses. One of these two nurses is required to be present for treatment of each patient with acute ischemic stroke, regardless of participation in a study. These nurses are familiar with all aspects of the proposed treatment methods and typical outcomes. The nurses will perform documented training on methods for obtaining consent and maintaining confidentiality of data obtained from subjects enrolled in research projects.

D. Study Procedures

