Pre-operative condition and patients outcomes will be assessed using standardized and validated measures. The primary endpoint of a mRS score will be obtained at least 90 days following treatment and again at 1 year following treatment. NIHSS score will be obtained in the emergency room before the treatment, within 24 h of treatment, and before discharge. The person who will obtain the NIHSS will be certified to obtain it. Adequacy of revascularization will be assessed at the end of treatment by the treating physician according the modified thrombolysis in cerebral infarction (mTICI) scale (see Appendix). All of these measures are standards for care and trials of acute ischemic stroke. [8-10] All case report forms will be maintained by the primary investigator at the local site, and stored within locked cabinets. The personal identifying information on the case report forms will be deidentified and assigned a code before being transferred to Akron General Medical Center for transfer of the data to a de-identified database which will be used for analysis.

IV. DATA COLLECTION

Version: 6.0

A. How and what data will be collected

Data related to patient demographics, stroke risk factors, condition prior to treatment, time of treatment, and outcomes will be collected for each patient. Data on demographics will include sex, age, and race. Data on stroke risk factors will include history of hypertension, blood pressure, prior heart attack, arrhythmias, diabetes, glucose (sugar) level at admission, and obesity. Data on condition prior to treatment will include NIHSS score determined in the emergency room. Data on time of treatment will include time from symptoms to arrival at emergency room, time to start of DCA, and time to end of the procedure. Data on outcomes will include mRS at 3 months, mRS at 1 year, NIHSS score within 24 hours and at discharge, and complications brain edema and intra-cranial hemorrhage. Other parameters within these categories could be acquired as deemed necessary for analysis of the data.

V. DATA ANALYSIS

A. Sample Size Considerations

Phase I

A power analysis has been performed based on the previous retrospective analyses of the relationship between outcomes and the CIS for phase I. The sample size was calculated for the influence of the combination of CIS and revascularization on good outcomes (mRS \leq 2) based on the following assumptions.

- The percentage of patients with fCIS will be 60%

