- The percentage of patients with good revascularization will be 50%
- The rate of good outcomes for the combination of fCIS and good revascularization is assumed to be 70%
- The rate of good outcomes for the combination of fCIS and poor revascularization is assumed to be 20%
- The rate of good outcomes for the combination of pCIS and good revascularization is assumed to be 20%
- The rate of good outcomes for the combination of pCIS and poor revascularization is assumed to be 10%

The assumptions provide the following power analysis:

- $\alpha = 0.05$ for overall analysis and set to 0.025 for subgroup analysis comparing fCIS and good revascularization to all other groups due to multiple comparisons
- power = 0.90
- Needed Sample size = 54 patients
- An additional 6 patients completing the trial are budgeted due to risk of errors in estimated outcomes. An additional 15-20 patients are expected to be enrolled due to patients lost to the 90 day follow up and/or deviations from the protocol.

Phase II

Phase II will be an exploratory study evaluating the rates for good outcomes for patients with pCIS treated with IVT plus IAT vs. IVT (or other standard of care) only. The rate of good outcomes is expected to be approximately 13% for the IAT group with revascularization. The investigators have no prior data on expected rates of good outcomes for patients with pCIS treated with IVT only. The best possible outcome rate would be on

Version: 6.0

the order of 25% noted previously for untreated acute ischemic stroke. Due to the low levels of good outcomes, the investigators acknowledge the study will be underpowered to detect a difference between the two treatment groups for a total sample size of 30. Phase II will serve as a pilot study to initially establish estimates of rates of good outcomes for pCIS patients treated with IVT only for design of a larger prospective study.

Genetic Analysis

Genetic analysis will be performed based on the following:

- Genetic and expression analysis for the two groups based on their collateral score
- Adjust groups for cardiovascular/stroke risk factor presence and other known confounding conditions
- High density SNP array analysis will be performed for common and rare alleles
 against known collateral-related genes that have been identified in mice. These
 include human RABEP2 and its isoform RABEP1 and related gene pathways;
 VEGFA, FLK1 and their related gene pathways; NOTCH, DLL4, ADAM10,

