 ADAM17, CNX37 and their related gene pathways.
- Subgroup analysis will be performed for ethnicities.
- Taqman assays and/or exome sequencing of significantly associated SNPs and/or genes.
- Pending results, a future validation study will follow this discovery study by increasing the sample size.

B. Statistical Methodology

Data for the proposed study will be analyzed using comparison of proportions and multivariable logistic regression. Analysis of proportions based on Fisher exact tests will be used to compare rates of good outcomes between the fCIS and pCIS groups as the primary end point for phase I. The influence of successful revascularization on outcomes for patients with fCIS or pCIS will also be analyzed using Fisher exact tests as the secondary end point.

Binary and/or ordinal multiple logistic regression analyses will be used to evaluate the influence of multiple parameters on the likelihood of a good outcome. These parameters will include CIS, mTICI score, NIHSS score, time to revascularization, age, sex, history of diabetes mellitus, history of high blood pressure, history of coronary artery disease. The same analyses will be performed for phase II, instead focusing on the treatment groups rather than the CIS classification.

VI. DATA AND SAFETY MONITORING PLAN

A. Describe any provisions for monitoring the data for safety

A safety committee will monitor the data. The safety committee will be composed of at least 3 voting members. At least two members will be neurologists, neuroradiologists or neurointerventionalists with experience treating acute ischemic stroke who are not investigators at any of the sites. These members will not be affiliated with the institution of the principal investigator, any sub- investigator, or Akron General Medical Center. At least one member with a background in biostatistics who is not an investigator or affiliated with Akron General Medical Center will also be on the committee.

For phase I, the only deviations in normal standards of care are:

Version: 6.0

- 1- the extra few minutes for full DCA for some centers as opposed to injecting only the occluded vessel
- 2- Adding IAT to treatment of patients seen between 6 and 24 hours of onset of symptoms.

The safety committee will be looking at known potential complications for IAT in both fCIS and pCIS groups. These include:

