- A. parenchymal hemorrhage type 2 symptomatic or asymptomatic hemorrhagic transformation within the vascular territory of the index ischemic stroke within 24 hours of treatment
- B. Any neurological worsening (NIHSS increase of 4 points or more) within 24 hours of treatment.

The rate of complications will be assessed by the safety committee after evaluation of 20, 30 and 40 patients. The trial will be stopped for safety if the rate of brain edema and intracranial hemorrhage is significantly larger for the pCIS group than the fCIS group.

The safety committee will meet at the end of phase I and give its recommendation to launch phase two or not depending on their review. The primary reason not to launch phase II would be higher than expected good outcomes for the pCIS patients treated with EVT plus standard of care, giving the indication that IAT should not be withheld from patients during phase II. During phase II, the safety committee will review the data on complications as noted above and percentage of good outcomes after 10 and 20 subjects are evaluated for comparisons between the two treatment groups.

VII. STUDY LIMITATIONS

A. Potential Limitations of Procedures

The primary limitation for phase II is the small sample size. Due to the expected relatively low rates of good outcomes for pCIS patients regardless of type of treatment, the power will not be sufficient to establish whether or not treatment with IAT is beneficial for patients with pCIS. The study will, however, provide the preliminary data needed to plan for a future, larger prospective clinical trial. Potential limitations for the genetic component of this study include DNA damage due to improper handling or storage of blood samples. The Paxgene DNA tubes are designed to stabilize DNA in the blood. However, the tubes will only function properly if the instructions for inverting the tube multiple times and prompt shipment for storage at Akron General are followed.

VIII. ETHICAL CONSIDERATIONS

A. Informed Consent

Enrollment of patients will be performed in an imaging suite at each institution. Once eligibility is determined by the treating physician based on imaging, the consent process will be initiated by a study research coordinator or study nurse. These investigators are familiar with all aspects of the proposed treatment methods and typical outcomes and maintaining confidentiality of data obtained from subjects enrolled in research projects.

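### Phase I's only written trial-level stopping condition compares two identically treated groups, so harm shared by both groups, or greater in fCIS, triggers it only by chance

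*Combined protocol and SAP*

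**What the plan says.** Section III.A says of the two Phase I groups: "Treatment will be identical for both groups". All patients get IAT plus standard care, so Phase I has no arm without IAT.

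Section VI.A sets the monitoring:

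- **Scope.** "The safety committee will be looking at known potential complications for IAT in both fCIS and pCIS groups". Two events are listed: parenchymal hemorrhage type 2, and "Any neurological worsening (NIHSS increase of 4 points or more) within 24 hours of treatment".
- **Looks.** The committee assesses complications once 20, 30 and 40 patients have been evaluated, then meets at the end of Phase I.
- **Stopping.** The trial is "stopped for safety if the rate of brain edema and intracranial hemorrhage is significantly larger for the pCIS group than the fCIS group". No test, significance level or expected rate is attached.
- **Phase II gate.** The committee advises on launching Phase II. The main stated reason not to launch is unexpectedly good pCIS outcomes.

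Section VIII.C adds a center-level trigger. Two or more events at a center lead to review, then possibly guidance or removal of that center.

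On timing, Section III.B defines the population as "within 8 hours of onset of symptoms". Section VI.A lists as a departure from normal care "Adding IAT to treatment of patients seen between 6 and 24 hours of onset of symptoms", and Section VIII.D describes the same 6-24 hour range.

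**The concern.** The rule asks whether pCIS patients fare worse than fCIS patients under the same treatment. That fits the worry in Section VIII.B that IAT may harm pCIS patients. If complications rise in both groups but more in pCIS, the rule can respond to a real difference. If they rise to a similar level in both, or more in fCIS, the contrast is null or points the other way, and the rule fires only through sampling error.

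The departures from usual care named in Section VI.A, a fuller angiogram and later IAT, apply regardless of CIS. Harm from either could therefore appear in both groups. Nothing in the plan ties a pooled rate, or the fCIS rate, to stopping the trial.

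Three weaknesses in the same text add to this:

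- **Events.** The rule's events only partly match the monitored list. Hemorrhage overlaps. Edema is collected (Section IV.A: "complications brain edema and intra-cranial hemorrhage") and listed with herniation or mass effect in Section VIII.C, but is not defined for the rule. NIHSS worsening is monitored but is not in the rule.
- **Late looks.** None is scheduled between 40 patients and the end of Phase I.
- **Counting.** The looks do not say whether enrolled patients or completers are counted.

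**Working it through.** **No plan figure to reproduce.** The stopping rule carries no number. The point itself is logical and needs none; the figures below only give it a scale.

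**Inputs from the plan.** Looks at 20, 30 and 40 (VI.A). A 60% fCIS share (V.A), giving fCIS/pCIS counts of 12/8, 18/12 and 24/16. Sixty completers (III.A). Up to 6 centers (III.A).

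**Assumed.** Fisher's exact test (used elsewhere in the plan for good outcomes), 0.05 at each look, and the complication rates.

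**1. A hand example at the first look.** With 0 of 12 fCIS and 3 of 8 pCIS events, Fisher's p = C(8,3)/C(20,3) = 56/1140 = 0.049, so the rule fires at 3 events in 20 patients. With 6 of 12 and 4 of 8, half of all patients have an event, the difference is zero, and no test can fire.

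**2. Current rule over three looks.** Let X and Y be the cumulative binomial counts in fCIS and pCIS. The stopping probability is the sum over looks of P(first look at which Y/n_p > X/n_f and p < 0.05), found by exact enumeration.

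| fCIS / pCIS rate | two-sided | one-sided |
|---|---|---|
| 20% / 20% | 3.3% | 3.5% |
| 30% / 30% | 3.1% | 3.8% |
| 40% / 40% | 2.7% | 4.2% |
| 40% / 20% | 0.1% | 0.1% |
| 20% / 40% | 27% | 31% |
| 30% / 60% | 43% | 53% |
| 5% / 20% | 25% | 25% |

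Doubling the rate in both groups from 20% to 40% leaves the stopping chance near the test's error level. For equal rates of 5-80% and splits from 50/50 to 70/30, Fisher gives 0.1-4.6%. A pooled z test gives from under 1% to 10.7%.

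**3. Center trigger.** Assume 6 equal centers and event rate q. With m patients at a center, P(fewer than 2 events) = (1-q)^m + m q (1-q)^(m-1). At 20 patients the centers hold 4, 4, 3, 3, 3 and 3. For q = 10% these terms are 0.9477 (m = 4) and 0.972 (m = 3), so P(some center flagged) = 1 - 0.9477² × 0.972⁴ = 0.198. At 30 and 40 patients it is 40% and 59%. For q = 40% it is 96% by 20 patients and over 99% by 30. A 40% rate would reach the committee, but a flag is also common at 10%, so it does not mark excess harm.

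**4. Exposure after the last scheduled look.** Counting completers: 60 - 40 = 20. Counting enrolled patients, Section V.A adds to the 60: "An additional 15-20 patients are expected to be enrolled due to patients lost to the 90 day follow up". That gives 75-80 enrolled, and 75 - 40 = 35 to 80 - 40 = 40.

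**5. Alternative rule.** Stop if the one-sided Clopper-Pearson lower bound exceeds a reference r, for the pooled rate or either group's rate. With x events in n patients, the 99% bound is the 1% quantile of Beta(x, n-x+1). Looks at 20, 30, 40 and 60, 60/40 split; r = 10, 15 and 20% for illustration only.

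| True situation | 99% bounds | 97.5% bounds |
|---|---|---|
| At reference (false stop) | 3.2-3.5% | 6-10% |
| +10 points in both | 39-56% | 57-68% |
| +20 points in both | 89-96% | 95-98% |
| +20 points in a quarter of patients (0.25 × 20 = +5 overall) | 15-22% | 27-32% |

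For the +10-point case, the current rule fires in 3.1-3.3% (one-sided 3.5-3.8%).

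**The case against.** The strongest reply is that harm is not going unmonitored. An independent committee with a biostatistics member sees complications in both groups at three looks, and naming one stopping condition does not bar it from recommending others. Section VIII.C lists a wider set of events, and by step 3 a 40% rate would almost surely reach the committee through center review. The Phase II advice rests on an overall review; good pCIS outcomes are the primary reason not to launch, not the only one. The size figures also partly restate a truism: a one-directional test fires at about its error rate when groups are equal.

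The importance of common harm is open too. Section I.A describes IAT within 8 hours as standard. If the 8-hour limit in Section III.B governs, much of any common harm is that of usual care.

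Finally, the remedy needs a reference rate the documents do not give (Section VIII.C says firm data on an accepted rate per operator are lacking), and it detects moderate or late-window harm poorly.

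Most of this stands as mitigation. It limits how much the gap matters. It does not supply a trial-level criterion for overall or fCIS harm. Center review ends in guidance or dropping a center, and the Phase II gate comes after Phase I exposure is complete.

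**Conclusion.** The concern holds. Followed as written, Phase I's only trial-level stopping condition does not respond to harm that is similar in both groups or greater in fCIS. The conclusion follows from the direction of the comparison and the identical treatment, and needs no assumed rate. Its illustrated size, at most 4.6% for equal rates under Fisher and up to 10.7% under a pooled z test, rests on an assumed 0.05 per look and assumed rates.

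The gap is in the pre-stated rule, not in the committee's access to data. It should be corrected, but it does not invalidate the design. How much it matters depends partly on how many patients receive late IAT. That cannot be judged until the 8-hour limit in Section III.B is reconciled with the 6-24 hour statements in Sections VI.A and VIII.D. The event definitions and the counting of evaluated patients are secondary drafting points.

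**What to change.** In Section VI.A:

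1. Add a trial-level criterion that judges the pooled complication rate and each CIS group's rate by exact one-sided lower bounds against a reference the safety committee sets in advance. No threshold is proposed here.
2. Keep the pCIS-fCIS comparison, with its test, sidedness and level stated.
3. Reconcile the rule's events with the monitored list and define them, including edema.
4. State whether looks count enrolled patients or completers, and schedule looks from 40 patients to the end of Phase I. With only the three current looks, 99% bounds detect a +10-point common excess in 29-39% of trials, against 39-56% when a look at 60 is added.
5. Tabulate events by time from onset, because a pooled bound dilutes harm confined to late patients.

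The cost is monitoring-plan wording, a few tabulations for a committee that already has a biostatistics member, agreement on a reference rate, and the false-stop chance in step 5 of the working. The bounds are reliable for a large common excess but not for a 10-point one, so committee judgement remains necessary.

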- 16. Khatri P, Yeatts SD, Mazighi M, Broderick JP, Liebeskind DS, Demchuk AM, et al. Time to angiographic reperfusion and clinical outcome after acute ischaemic stroke: an analysis of

Version: 6.0

data from the Interventional Management of Stroke (IMS III) phase 3 trial. The Lancet Neurology. 2014; 13:567-74.

Version: 6.0

XI. APPENDICES

MODIFIED RANKING SCORE

SCORE	DESCRIPTION
0	No symptoms at all
1	No significant disability despite symptoms; able to carry out all usual duties and activities
2	Slight disability; unable to carry out all previous activities, but able to look after own affairs without assistance
3	Moderate disability; requiring some help, but able to walk without assistance
4	Moderately severe disability; unable to walk without assistance and unable to attend to own bodily needs without assistance
5	Severe disability; bedridden, incontinent and requiring constant nursing care and attention
6	Dead

Modified thrombolysis in cerebral infarction (mTICI) scale

- 0: No perfusion
- 1: Perfusion past the initial obstruction but limited distal branch filling with little or slow distal perfusion
- 2a: Perfusion of less than half of the vascular distribution of the occluded artery
- 2b: Perfusion of half or greater of the vascular distribution of the occluded artery
- 3: Full perfusion with filling of all distal branches

Version: 6.0 Date: 03/30/2018

Integrated Acute Stroke Flowsheet National Institutes of Health Stroke Scale

Complete a full assessment TID during the first 72 hours after admission for stroke, with any decline in neurological status, and when the patient is received from ER, ICU, or PACU into 6NW or 6 Observation. After the 72 hour period, a full assessment should be completed with any changes in neurological status, and prior to discharge.

Complete a modified assessment (the shaded sections, and any other area of concern) when the neurological assessment is required more often than TID.

Administer NIHSS in order listed. Record performance in each category after each subscale exam. Do not go back and change scores. Scores should reflect what the patient does, and not what the clinician thinks the patient can do.

Except where indicated, the patient should not be coached (i.e. repeated requests to patient to make a special effort).

		S C	Date/T ime	Date/T ime	Date/T ime	Date/ ime
CATEGORY	Description					
1a. Level of consciousness	Alert, keenly responsive	e 0				
***(Patients who score 2 or 3 on this item,	Not alert (arousable by minor stimulation to obey, answer, or respond)	1				
should be assessed using the Glasgow Coma	Not alert (responds to repeated or painful stimulation)	2				
Scale)	Only reflex motor, autonomic effects, or totally unresponsive	3				
1b. LOC, questions	Answers both questions correctly	0				
(month, age)	Answers one question correctly	1				
	Answers neither question correctly	2				
1c. LOC, commands	Performs both tasks correctly	0				
(Open/close eyes, make fist,	Performs one task correctly	1				
release fist) Pantomime may be used	Performs neither task correctly	2				
2. Best gaze	Normal	0				
(Patient follows examiner's finger or face	Partial gaze palsy	1				
through full horizontal field)	Forced deviation (deviation not overcome by oculocephalic maneuver)	2				
3. Visual	No visual loss	0				
(Introduce visual stimulus/threat to patient's field	Partial hemianopia (sector or quadrant field deficit)	1				
quadrants)	Complete hemianopia (dense field loss, such as half of visual field)	2				
1	Bilateral hemianopia (blind)	3				
4. Facial palsy	Normal	0				
(Show teeth, raise eyebrows,	Minor paralysis (mild asymmetry on smiling)	1	l			
squeeze eyes shut) Pantomime may be used	Partial paralysis (paralysis of lower face)	2	l			1
	Complete (one or both sides: paralysis of upper and lower face)	3				
5a. Motor arm - Left	No drift (limb holds for full 10 seconds)	0				
(Test each limb independently: Palm Down: Drift (limb drifts downward but does not fall to rest on a support)						
Elevate arm to 90° if pt sitting, 45° if pt supine	Some effort against gravity (drifts to fall on support)	1 2				
and score drift/movement over 10 seconds)	No effort against gravity (trace movement, limb falls immediately)	3				
5b. Motor arm – Right No voluntary movement No voluntary movement		4				
(As above) Amputation, joint fusion etc		X				
6a. Motor leg - Left	No drift (limb holds for full 5 seconds)	0				
(Test each limb independently: With pt supine,	Drift (limb drifts downward but does not fall to rest on a support)	1				
elevate extremity to 30° and score	Some effort against gravity (drifts to fall on support)	2				
drift/movement over 5 seconds)	No effort against gravity (trace movement, limb falls immediately)	3				
6b. Motor leg - Right	No voluntary movement	4				
(As above)	Amputation, joint fusion etc	X				
7. Limb ataxia	Absent	0				
(Finger-nose, heel down shin)	Present in one limb	1				
	Present in two limbs	2				
8. Sensory	Normal	0				
(Pin prick to face, arm, trunk, and leg – compare	Mild to moderate sensory loss (less sharp/dullness)	1				
side to side) Look at grimace in aphasic patient	Severe or total sensory loss (not aware of touch)	2				
9. Best language	No aphasia	0				
(Name item, describe a picture and read	Mild to moderate aphasia (reduced fluency or comprehension)	1				
sentences)	Severe aphasia (communication exchange very limited)	2				
	Mute, global aphasia	0				
10. Dysarthria Normal articulation					I	1
(Evaluate speech clarity by having patient read or	Mild to moderate dysarthria (can be understood)	1	l			1
repeat listed words)	Severe dysarthria (unintelligible or worse)	2	1		I	1
	Intubated or other physical barrier	X				
11. Extinction and Inattention No abnormality (no neglect)			l			
(Use information from prior testing to identify Visual, tactile, auditory, spatial, or personal inattention, or						
neglect or double simultaneous stimuli testing) extinction to bilateral stimulation in one of the sensory modalities)			l			1
	Profound: more than one modality affected	2		-		-
	TOTAL SCO			-		-
PUPILS • • •		1011				
Sizes: 1mm 2mm 3mm 4mr	n 5mm 6mm 7mm 8mm 9mm Right Size/React	ion				
	ion: ± normal Schuggish absort!					
	ion: + normal S sluggish - absent Signature on back side of page. Initials of exami					

Version: 6.0 17
